Simple Physical Activity Questionnaire. The SIMPAQ (48) is an interview tool designed to measure time spent in bed, time spent exercising, and time spent in physical activity. Participants' physical activity level will be measured at Study Visit #2 only.

Profile of Mood States. The POMS (45) is a 65-item questionnaire using a 5-point Likert-type scale ranging from 0 "not at all" to 4 "extremely." It will be used to determine the mood state of participants which include: tension, depression, confusion, anger, fatigue, vigor, and total mood disturbance. Internal consistencies for the subscales on the POMS range from .84 to .95 (42). To assess the mood-response to exercise, participants will complete the POMS pre- and post-exercise (Study Visit #2 and #3).

Ratings of Perceived Exertion (RPE). A validated RPE scale (46) will be used to measure the perceived intensity of the exercise during Study Visit #2 and #3. The scale ranges from 6 "no exertion at all" to 20 "maximal exertion."

Short-Form McGill Pain Questionnaire. The SF-MPQ (47) is a 15-item survey with items rated on a 4-point scale ranging from 0 "none" to 3 "severe." Eleven items assess the intensity of sensory components of pain and four items assess the intensity of affective components of pain. In addition, a Present Pain Index (PPI) and a Visual Analogue Scale (VAS) are included in the questionnaire. This questionnaire will be administered pre- and post-exercise during Study Visit #2 and #3 to assess the pain response to exercise.

State-Trait Anxiety Inventory. The STAI Form Y-1 (49) is a 20-item questionnaire designed to measure state anxiety. Items ranged from 1 "almost never" to 4 "almost always" with higher scores indicating higher anxiety. The internal consistency for the STAI ranges from .86 to .95. Participants will complete the STAI pre- and post-exercise during Study Visit #2 and #3.

VAS Neuropathic Pain Sensations. Visual analog scales (VAS) will be used to assess the intensity of the following sensations specific to neuropathic pain: pins and needles, tingles, stinging, and electrical pain sensations. This questionnaire will be administered pre- and post-exercise during Study Visit #2 and #3.

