Quantitative Sensory Testing (QST). Pain sensitivity will be assessed via QST which represents a non-invasive set of psychophysical tests that are designed to measure different aspects of the sensory nervous system (50, 51). Pre-clinical and clinical research indicates that breast cancer survivors with CIPN experience altered sensations such as cold allodynia, heat hypoalgesia, and/or mechanical allodynia (25). By using standardized procedures (51, 52), researchers and clinicians can examine these altered sensations through testing the function of specific nerve fibers. Further, these methods can help us understand the role of peripheral (i.e., excitability of peripheral nerves) or central sensitization (i.e., excitability of neurons in the central nervous system) in pain transmission. By using QST to evaluate pain responses, we will gain deeper insight into the treatment potential of exercise in this population. Therefore, our QST protocol will involve the assessment of mechanical allodynia and hyperesthesia, mechanical pain threshold, thermal (hot and cold) pain thresholds, pressure pain threshold, vibration detection threshold, and mechanical temporal summation.

- Mechanical allodynia (presence of pain in response to a stimulus that would be rated non-painful under normal conditions) and hyperesthesia (perception of sensation out of proportion to the applied stimulus) will be assessed by applying stimuli to both the control and test site. Participants will be asked to rate their pain (i.e., intensity, unpleasantness) after each stimulus. Mechanical allodynia will be assessed by applying light touch, using a Q-tip, on a 2-cm area of skin for approximately 2 s (43). Hyperesthesia will be assessed by a pinprick test using the Neuropen. The Neuropen is a spring-loaded device in which a pin (diameter less than 0.4 mm) is placed inside a guide which allows relative standardization of the degree of force applied (approx. 40 g) (53).
- Pain sensitivity, or a heightened pain response, will be assessed by determining pain thresholds to different stimuli. Pain thresholds will be assessed by applying, to a site close to the affected area (e.g., wrist or ankle areas), von Frey filaments (for mechanical pain threshold), a Medoc Thermal Sensory probe (for thermal pain thresholds), and an algometer (for pressure pain threshold) until the participant indicates the stimulus to be painful.

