- Mechanical temporal summation, which is a measure of central sensitization, will be assessed using a standardized protocol on both the control and test sites (51). In order to determine summation, participants will rate pain intensity and unpleasantness after a single mechanical stimuli (i.e., pinprick) and after a series of 10 administered at 1-second intervals.
- Vibration detection threshold is indicative of activation of nerve fibers which do not typically transmit pain information. However, under some pathological conditions, such as CIPN, these fibers begin to send pain signals. It will be determined using a Rydel-Seiffer (R-S) graduated tuning fork which has a graduated scale (1-8) that, when activated, accurately represent the amplitude of vibration (54). The activated R-S tuning fork will be placed on the skin and participants will indicate when the vibration is no longer felt. The research assistant will record the visible score from the fork at that instant.

A test site (i.e., a site near the affected area such as wrist or ankles) and a control site (i.e., non-painful site on the opposite limb) will be chosen for each participant during the familiarization session. In addition to this, participants will undergo practice tests using an abbreviated protocol prior to experimental testing. The researchers will instruct participants to report anytime they experience “intolerable pain” which is defined as the point at which they do not want the test to continue. Upon report of “intolerable pain,” the test will immediately stop, and the patient can decide to continue to the next test or to skip the remaining tests. [name] will provide training for these procedures.

Procedures

Prior to attending the study visits, volunteer eligibility will be determined through a preliminary phone screen. If the volunteer is eligible, they will be scheduled for the familiarization session. Eligibility will be further assessed at the familiarization session (Visit 1) to ensure that the participant understands how to use the safety features on the treadmill, and the participant’s pain is neuropathic and results from chemotherapy administration. Upon completion of the familiarization session, participants will be scheduled for Study Visit #2 and will be asked to refrain from exercise for 24 hours and to refrain from drinking or eating (except for water) for 2

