The design of this study is an exploratory within subject, repeated measure design where participants complete pre-post measures during two study visits (i.e., aerobic and yoga tasks). Descriptive statistics will be reported on the demographic variables (i.e., age, ethnicity, height, etc.) and CIPN (i.e., painDETECT and pain diagram questionnaires) to characterize the sample. RPE and HR data will be summarized to describe the exercise stimuli. We will conduct condition (aerobic, yoga) x time (pre-, post-) repeated measures ANOVAs to determine the influence of yoga and aerobic exercise on pain (QST outcomes, SF-MPQ, and VASs), psychological outcomes (POMS, STAI), and eCBs (2-AG, AEA). Further, effect sizes for pre-post changes in dependent variables will be calculated using Cohen's d to understand the strength of the effect. Significant interaction effects will be examined using simple effects and Holm's procedure will be applied. Data which violate the assumption of normality will be logarithmically transformed.

Study Coordination

This study will involve collaboration between the University of Wisconsin-Madison and the Medical College of Wisconsin. The University of Wisconsin-Madison will serve as the lead site for this study, thus [name], PI, will oversee all study activities. In addition, she will be responsible for coordinating between UW-Madison and the Medical College of Wisconsin.

Procedures involving recruitment will be conducted at the University of Wisconsin-Madison and will be supervised by [name]. Data collection and data analysis will be conducted at UW-Madison under the supervision of [name]. Analysis of the blood samples will be conducted at the Medical College of Wisconsin under the supervision of [name]. These samples will be shipped to [name] who will supervise the eCB assays. [name] and [name] will communicate using email throughout the duration of eCB assay process. [name] has visited [name] lab several times and they have previously collaborated in eight prior studies.

Data Collection

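### Does the log transform for non-normal data need a written rule for scores of zero?

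*Combined protocol and SAP*

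**What the plan says.** The Data Analysis section plans condition by time repeated measures ANOVAs for "pain (QST outcomes, SF-MPQ, and VASs), psychological outcomes (POMS, STAI), and eCBs (2-AG, AEA"), and then states: "Data which violate the assumption of normality will be logarithmically transformed". It gives no added constant, no fallback method and no criterion for a violation, and no other section does.

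The Instruments section shows which outcomes can be zero. The SF-MPQ "is a 15-item survey with items rated on a 4-point scale ranging from 0" to 3, and "four items assess the intensity of affective components of pain". The POMS is scored "using a 5-point Likert-type scale ranging from 0" to 4. STAI items start at 1, so with 20 items the lowest score is 20. Vibration is read from a "graduated tuning fork which has a graduated scale (1-8").

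For other outcomes the plan does not settle the matter. The anchors of the symptom VASs and of the touch-pain ratings are not given. Temporal summation uses ratings "after a single mechanical stimuli (i.e., pinprick) and after a series of 10", without saying whether the two are subtracted.

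**The concern.** The logarithm of zero is undefined, so the one stated remedy cannot be applied as written to valid SF-MPQ or POMS scores. Each participant contributes four cells (two sessions, before and after). If a zero becomes a missing value and only complete participants are used, one zero removes the person from that outcome. Some of those removed would be people whose pain fell to nothing after exercise, which is the response the trial looks for. The other route is to add a constant, and the plan does not fix one, so it could be chosen after the data are seen. With a stated sample size of 10, losing several participants would matter, and two readings of the same sentence could give different verdicts at the .05 level.

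**Working it through.** **1. The plan's own figure.** Sample Size Justification gives f = 0.4, alpha = .05, power = .80 and N = 10. For a within-subject factor, λ = f²·N·m/(1−ρ). With one group, m = 4 measurements, ρ = 0.5 and no sphericity correction (m, ρ and the correction are assumptions), λ = 0.16 × 10 × 4 / 0.5 = 12.8 on 3 and 27 degrees of freedom, and power is 0.806. N = 10 reproduces and is used below.

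**2. Where normality is assumed.** In a 2×2 within-subject ANOVA each effect has one degree of freedom, and its F is the square of a one-sample t on a within-person contrast. The assumption therefore concerns the contrasts, although the sentence in the plan could also be read as referring to raw cells. Both readings were run, using Shapiro-Wilk p < .05 as the trigger.

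**3. Simulation inputs (all assumed).** Four equally correlated normal scores per person, rounded and clipped to the scale; ρ = 0.5 or 0.8; a fall of 0.5 SD in both sessions; 8,000 trials. A cell is zero when the latent score is below 0.5:
- Affective subscale (4 × 3 = 12 maximum), mean 3, SD 3: Φ((0.5−3)/3) = 0.20 before and Φ((0.5−1.5)/3) = 0.37 after; average 29%.
- Total (15 × 3 = 45 maximum), mean 10, SD 7: Φ(−9.5/7) = 0.09 and Φ(−6/7) = 0.20; average 14%.
- Total, mean 15, SD 8: Φ(−14.5/8) = 0.03 and Φ(−10.5/8) = 0.09; average 6–7%.

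**4. Power for the time effect, N = 10 (ρ = 0.5 / 0.8).**

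| Outcome | Untransformed | Zeros dropped, raw-cell check | Zeros dropped, contrast check | log(x+1), raw-cell check |
|---|---|---|---|---|
| Affective, 29% zeros | 0.45 / 0.76 | 0.17 / 0.44 | 0.42 / 0.70 | 0.45 / 0.74 |
| Total, 14% zeros | 0.49 / 0.85 | 0.37 / 0.73 | 0.48 / 0.83 | 0.48 / 0.83 |
| Total, 6–7% zeros | 0.51 / 0.86 | 0.47 / 0.82 | 0.50 / 0.85 | not run |

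On the affective subscale the raw-cell check fires in 81% / 75% of trials and the contrast check in 9% / 15%. For the interaction (a 1 SD fall in yoga only, affective subscale) power is 0.36 / 0.65 untransformed, 0.11 / 0.32 with zeros dropped after a raw-cell check, and 0.34 / 0.61 after a contrast check. Repeating the affective time-effect runs with fresh random draws moved the figures by no more than 0.02.

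**5. Choice of constant.** A fall from 5 to 0 is ln(6/1) = 1.79 with +1, ln(5.5/0.5) = 2.40 with +0.5 and ln(5.1/0.1) = 3.93 with +0.1, so the constant does change the weight of a zero. The effect on verdicts is modest: on the affective subscale, 0.5 against 1 changes the .05 verdict in 3% / 3% of trials (raw-cell check) or under 1% (contrast check); 0.1 against 1 changes 8% / 9% or 1% / 2%.

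**6. Error rate and bias.** With no true effect, rejection rates on the affective subscale are 0.044 / 0.044 with zeros dropped and 0.052 / 0.045 with log(x+1). The mean raw fall is 1.15 / 1.33 points among those kept and 1.16 / 1.15 among all, so deletion costs precision and does not hide the benefit.

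**The case for a change.** The strongest case for a change is that deletion can follow from the literal wording without anyone deciding on it: a log of zero is returned as missing or infinite, and a classical repeated measures ANOVA uses complete participants. On the affective subscale only 4.1 / 5.1 of 10 people would remain. About two thirds of those dropped (68% / 65%) went from above zero to zero in at least one session. Dropping and log(x+1) disagree at .05 in 34% / 35% of trials after a raw-cell check. Recruiting more does not cure it: at N = 20 power is 0.79 / 0.98 untransformed against 0.30 / 0.75 with deletion, and at N = 30 it is 0.92 / 1.00 against 0.45 / 0.92. The loss does not depend on this one model either. With right-skewed scores, a 1.2 SD yoga-only effect and 5% zeros per cell before the effect, deletion gives 0.34 against 0.61 for log(x+1). The inclusion criteria require painful polyneuropathy, but no minimum SF-MPQ or POMS score. A written rule would cost one sentence.

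What stands is that the plan is silent and that careless handling could be costly. What does not stand is that such handling is likely to pass unnoticed. Where the cost is large, more than half of 10 participants vanish from the analysis at ρ = 0.5 and the error degrees of freedom fall from 9 to about 3, which an analyst will see. Where few people would be lost, as with the total at 6–7% zeros, power moves only from 0.51 to 0.47 even in the worst handling. The heavy-zero example is also a subscale; the Data Analysis section lists the SF-MPQ without saying that its subscales are analysed separately. After a contrast check, dropping and log(x+1) disagree in only 4% / 7% of trials.

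**Conclusion.** No change follows. The plan leaves out a rule for zeros, but an analyst has to supply one on meeting the first zero, and the ordinary choice, log(x+1), gives 0.45 / 0.74 against 0.45 / 0.76 untransformed. The fall to 0.17 / 0.44 appears only when deletion, a raw-cell check and frequent zeros coincide, and the documents call for none of these. A more elaborate rule brings no gain: leaving zero-bounded scores untransformed, with a sign-flip permutation test when the contrast check fails, gives 0.45 / 0.75 against 0.45 / 0.76 for log(x+1) under the same check. It would also have to say which of the three contrasts triggers the switch.

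The weight is low for a further reason: the study is described as an exploratory pilot, no outcome is named as primary, and Cohen's d is reported for pre-post changes beside the tests. STAI and vibration are unaffected, as are AEA and 2-AG when above zero.

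Every zero rate, mean, SD, correlation and effect size above is an assumption, because the documents give no score distributions. No POMS figures were run; the POMS point rests only on its items starting at 0. The VAS, touch-pain and temporal summation points depend on anchors and scoring that the plan does not state, and they add no weight here.

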hours prior to their study visit. Participants will attend one familiarization session, 45 minutes long, and two study visits, each 60-75 minutes long, to complete both the yoga and aerobic exercise sessions. There will be between 2 and 7 days between Study Visit #2 and Study Visit #3. All visits will be completed independently and participants will spend a total of 165-195 minutes completing this study. Session order (experimental vs. aerobic exercise) will be randomized and counter-balanced. See Figure 1 for a schematic of the study procedures.

The exercise stimuli will be matched on session duration (i.e., 40 minutes) and session intensity (using the ratings of perceived exertion scale, RPE).

Yoga Task: The yoga task will consist of 44 minutes of Iyengar yoga in a sound-dampened chamber. The yoga session will be pre-recorded and led by a certified yoga instructor who has previously worked with individuals with chronic medical conditions. The yoga task will consist of 7 minutes of light intensity poses (i.e., RPE 10-11) followed by 32 minutes of moderate intensity poses (RPE 12-14). The cool-down will consist of 5 minutes of light intensity poses (RPE 10-11). Participants will follow the pre-recorded video and will be instructed to participate to the best of her ability. Heart rate (HR) will be recorded continuously through a heart rate monitor and the session intensity and pain intensity will be recorded every five minutes. Session intensity will be monitored using the ratings of perceived exertion scale (RPE) (46). Pain intensity will be recorded using one item rated on a 0-10 scale from the painDETECT (42): “How would you assess your pain now, at this moment?” Participants will be encouraged to work at a moderate intensity for the 32 minute time period.

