abbreviated QST protocol. Subsequently, participants will walk on the treadmill for 5 minutes (aerobic task) and will practice the different yoga poses (yoga task) in order to be familiarized with the exercise stimuli. Thus, participants will have a better understanding of what to expect in the coming study visits. Lastly, participants will be asked to wear an accelerometer for 7 days to objectively determine average levels of physical activity. Participants will also be asked to complete an activity log in conjunction with wearing the accelerometer. Participants will return the accelerometers and activity logs one week later when they return for their second visit.

Visit 2

Participants will be randomly assigned to complete the yoga or aerobic task prior to coming in for Study Visit #2. All study visits will be completed in the Exercise Psychology Laboratory in the University of Wisconsin-Madison Natatorium building (note: numerous exercise studies have been completed in this lab without incident). Upon arrival, participants will complete the Simple Physical Activity Questionnaire (SIMPAQ) and a packet of mood questionnaires consisting of: the short-form McGill Pain Questionnaire (SF-MPQ), the Profile of Mood States (POMS), the State-Trait Anxiety Inventory (STAI), and 4 visual analog scales (VAS) which measure different aspects of neuropathic pain (i.e., pins and needles, tingles, stinging, electrical pain sensations) after which they will be outfitted with a heart rate monitor and a research assistant will explain the RPE scale. Next, participants will have their blood drawn (5 ml) and will undergo the QST protocol. They will then be informed of their study visit task (yoga or aerobic exercise task) and be instructed to complete the task in a sound-dampened chamber (yoga) or on the treadmill (aerobic exercise). Immediately upon task completion, the participants will have their blood drawn (5 ml) and will undergo the QST protocol. Lastly, the participants will complete the same questionnaires listed previously (SF-MPQ, POMS, STAI, and the pain sensation VASs). Blood samples will be prepared for analysis within 10 minutes of collection (see 'Endocannabinoid Assays' section below).

Visit 3

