downloaded from the device will be linked to each participants' unique study ID number. No information or data goes to the company (ActiGraph) that produces/sells the devices. After the devices are returned and downloaded, data will be deleted off of the accelerometer. Data will be imputed into a computer for data analysis where it will be stored in a secured file on the Exercise Psychology Lab server which is located in a password protected area with firewall protection and backed up daily. All team members will have access to the coded information located in the Exercise Psychology Laboratory. Biological samples (blood samples) will be stored in a freezer in the Biodynamics Laboratory located in the Natatorium at the University of Wisconsin-Madison after which they will be transferred to a container of dry ice and driven by the PI to [name] laboratory at the Medical College of Wisconsin. The blood samples then will be stored in [name] lab after which they will be exhausted. The blood samples will contain only the participant ID number, time of collection, and session date; thus, participants will not be able to be identified. Moreover, data for eligible participants will be kept and secured in a locked file cabinet in the Exercise Psychology Lab until the participant has either completed the study, removed themselves from participation, or is excluded from participation. If participants give consent to be contacted for future research, their contact information and screening data will be stored in a locked cabinet in the PI's office once the study is complete (see "Permission to Contact for Future Research List" section below for more information). All other screening data for eligible participants will be shredded upon participant completion, dropout, or exclusion of the study. Phone screening data from any interested potential participants not meeting inclusion criteria will be shredded immediately. Biological samples will be exhausted upon completion of endocannabinoid assay. Any link between coded data and directly identifiable data (i.e., names/phone number/email on the informed consent) will be shredded after 7 years. Coded data includes all data collected for the purposes of the study (i.e., questionnaire data, exercise data, accelerometer data, eCB results, and QST data) and will be kept indefinitely.

Permission to Contact for Future Research List

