A permission to contact list will be generated from participants who provide consent to be contact for future studies. This list will consist of the contact information and screening data from only these individuals. The information will be stored in a locked cabinet in the PI's office. Only participants who are interested in the current study will be on the "permission to contact for future research" list and only the study team will have access to this list. Further, it will only be used to recruit for similar studies in the Exercise Psychology Laboratory. The list will be destroyed after 5 years. Generating this list will be helpful in recruiting breast cancer survivors with CIPN for future studies conducted by [name] Psychology Lab.

Sample/Specimen Collection

Blood samples will be collected by a trained phlebotomist using EDTA containing tubes (BD Vacutainer, K3E EDTA K3) and centrifuged. Plasma will be frozen at -80 C in a freezer in a designated area on the UW-Madison campus until all samples are collected. All samples will be driven by the PI to [name] lab at the Medical College of Wisconsin and will be stored in a freezer until analysis. No samples will include identifiable information and the results from the eCB assays will be shared between study team members using the participant ID numbers.

Study Procedures

[figure not shown]

Figure 1. Study flow chart.

References

1. American Cancer Society. Breast Cancer Facts & Figures 2017-2018. In. Atlanta: American Cancer Society, Inc.; 2017.

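### The blood sample label lets the assay laboratory tell pre-exercise from post-exercise samples, and the plan states no masking of the assay

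*Combined protocol and SAP*

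**What the plan says.** The Data Collection section fixes the label: "The blood samples will contain only the participant ID number, time of collection, and session date". The reason given there is that participants cannot then be identified.

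Under Procedures, Visit 2, the first draw comes before the task: "Next, participants will have their blood drawn (5 ml) and will undergo the QST protocol". A second 5 ml draw follows as soon as the task ends. Visit 3 repeats this pattern. The visits fall on different dates: "There will be between 2 and 7 days between Study Visit #2 and Study Visit #3". Session order is randomized and counterbalanced.

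On reporting, the Sample/Specimen Collection section says that "the results from the eCB assays will be shared between study team members using the participant ID numbers". It also says that plasma stays frozen at the lead site until collection is complete and is then taken to the assay site together.

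The Data Analysis section plans a condition x time repeated measures ANOVA for 2-AG and AEA, and Cohen's d for pre-post changes. The documents do not mention masking of assay staff, recoding of samples, run order, or a rule for repeating or rejecting an assay value.

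**The concern.** AEA and 2-AG are the endocannabinoid outcomes named for Aim 2. The Study Objectives and Study Significance sections state the expected direction, a rise after exercise. Time point is one of the two ANOVA factors and the whole basis of the pre-post Cohen's d.

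A quantitative assay still involves some judgement, for example in peak integration, in repeating a run or in setting a value aside. If the person deciding can see which sample is post-exercise, a reader cannot exclude that the decision leaned in the expected direction. The label was designed to protect identity, and it does. It was not designed to mask, and a label that protects identity equally well can also conceal the time point.

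**Working it through.** **1. What the label reveals.** Inputs: label content (Data Collection); one draw before and one straight after each task (Visits 2 and 3); task length (Yoga Task: "The yoga task will consist of 44 minutes of Iyengar yoga"; the matched duration is elsewhere given as 40 minutes); 2 to 7 days between visits.

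- ID plus date selects the two tubes of one visit.
- Their clock times differ by at least the task length, 40 or 44 minutes. Sensory testing also falls between the first draw and the task. The earlier tube is therefore pre and the later is post, and no key is needed.
- Samples: 4 per participant, so 4 x 10 = 40 samples in 20 pairs at N = 10. The ceiling is 4 x 30 = 120 samples in 60 pairs if all 30 recruits completed, which the plan does not expect.
- Every complete pair can be classified from the label. With a random code and the key held elsewhere, a pair can only be guessed, with probability 0.5.

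**2. What the label does not reveal.** Modality is not on it. The date shows which visit came first, but order is randomized, so the date alone does not indicate yoga or aerobic exercise.

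**3. Which estimates are exposed.** Let Y and A be the true mean pre-post changes for yoga and aerobic exercise, and let b be a handling shift that depends on time point only.

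- Time effect: ((Y + b) + (A + b))/2 = (Y + A)/2 + b. The shift remains.
- Pre-post Cohen's d within a session: b enters the numerator. The shift remains.
- Condition x time: (Y + b) - (A + b) = Y - A. The shift cancels.

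**4. The plan's own figure.** The only design figure is N = 10 (Sample Size Justification: f = 0.4, alpha = .05, power = .80). Assume four measurements and a correlation of 0.5, neither of which is stated. The noncentrality is then 10 x 4 x 0.4² / (1 - 0.5) = 12.8 on 3 and 27 degrees of freedom, and power is 0.806, so N = 10 is reproduced. The present point does not depend on this figure, and the fix does not change it.

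**5. Illustrative size.** The documents give no bias estimate, so the shift is an assumption, with a range that includes zero. For a two-sided 5% paired t-test at N = 10 with no true change, the critical value is 2.262 on 9 degrees of freedom, and the noncentrality is shift x √10.

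| Assumed shift (SD of the change) | Noncentrality | False-positive rate |
|---|---|---|
| 0 | 0 | 5.0% |
| 0.05 | 0.158 | 5.2% |
| 0.10 | 0.316 | 5.9% |

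**The case against.** The strongest reply is that a label is not a laboratory procedure. The documents do not say what the assay operator sees, in what order samples are run, or whether the laboratory recodes on receipt. The Endocannabinoid Assays section refers to a standardized protocol in a cited source that is not reproduced. This stands. A reader might infer that the Aim 2 outcomes are in fact measured unmasked, but the documents support only that the label permits it and that no masking is stated.

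A reader might also infer that the laboratory knows the modality, because "All team members will have access to the coded information located in the Exercise Psychology Laboratory" and the coded data include exercise data. That sentence concerns records held at the lead site, and the assay is done at another institution. The team list includes an investigator there, but nothing says that those running the assay would consult the exercise records. The documents therefore do not support the claim that the yoga-versus-aerobic comparison is compromised.

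Nor do they support the inference that doubtful values will be discussed or repeated with the time point known. The Study Coordination section says only that two team members "will communicate using email throughout the duration of eCB assay process"; it does not say what about.

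Two further replies carry weight. Isotope-dilution LC-MS-MS leaves little room for judgement, and the study calls itself an exploratory pilot. Relabelling also has an error of its own. One swapped pair among 10 changes that pair's expected contribution from +d to -d and so lowers the expected mean change by 2d/10. With d = 0.2, an assumed value for a small effect, that is 0.04 SD, close to the 0.05 SD shift illustrated above. A check of the link list is therefore needed.

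None of this removes the core point. The plan specifies a label that shows time point, and a label that does not would serve privacy just as well.

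**Conclusion.** The point holds as a minor, cheap improvement. From the stated label and draw schedule, pre and post can be read for every complete pair, and the plan contains nothing that masks the assay. The exposure is limited to the time effect and the pre-post Cohen's d for AEA and 2-AG. The condition x time interaction is unaffected so long as any shift is equal in both sessions.

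The size is unknown and probably small. The range of 5.0% to 5.9% for the false-positive rate at N = 10 rests entirely on an assumed shift of 0 to 0.10 SD of the change. The documents contain no evidence that any shift would occur.

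**What to change.** Amend two places: the label sentence in Data Collection, and the sentence on sharing results in Sample/Specimen Collection. The amended text should say that:

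- before transfer, each plasma aliquot is relabelled with a random sample number that carries no ID, date or time;
- the list linking sample number to participant, visit and time point stays at the lead site;
- each participant's four samples are run together, in random-number order;
- results are returned, and any decision to repeat or reject a value is made, by sample number;
- the link is released only after the assay file is locked.

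The cost is two amended sentences and about 40 labels at N = 10 (at most 120). Because plasma is already held until collection ends, relabelling can be done in one step. Visits, sample size, power and clinical procedures do not change. The downside is a small risk of an error in the link list, controlled by having a second person check the list before transfer.
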